6.3.2. Potential Benefits

Immediate potential benefits include a focused effort by the research team to visualize the stomach for all subjects and help ensure appropriate follow-up. Long-term potential benefits include more effective and efficient management of a variety of conditions that are common in the population.

Recently, the advantage of diagnostic tools that decrease exposure of healthcare providers to infectious diseases such as COVID-19 has become clearer.

6.3.3. Discussion

The evaluation of suspected symptoms in the stomach often requires an EGD by a gastroenterologist or surgeon and which may also entail hospitalization and procedural sedation by an anesthesiologist. While this traditional process is safe and effective, it is not efficient for low-risk patients and not timely for all high-risk patients. The opportunity to bring NaviCam MCC to the front-lines of US medical care may change how we manage GI symptoms. This trial is an important step toward demonstrating that NaviCam MCC is a safe and effective tool to diagnose patients who have upper GI symptoms and improve quality of care for those patients.

7. OBJECTIVES

7.1. Primary Objective

- ✓ Aim 1) To demonstrate feasibility of MCC in an outpatient setting for patients with upper abdominal symptoms
- ✓ Aim 2) To demonstrate high-quality visualization of gastric anatomic regions.
- ✓ Aim 3) To pilot a comparison of MCC versus EGD regarding the ability to visualize both gastric anatomic regions and gastric lesions.

7.2. Secondary Objective

- 1) To perform a cost-effective analysis of MCC v EGD.
- 2) To measure patient satisfaction for EGD v MCC.
- 3) To measure 30-day safety.
- 4) To compare international trials that compared EGD to MCC for detection of gastric lesions.
- 5) To measure the time required to visualize the stomach for MCC versus EGD.

8. STUDY OUTCOME MEASURES

8.1. Primary Outcome:

Aim 1: Pilot and Feasibility Stage.

- 1) *Implementation:* Installation, Training, Site Requirements
- 2) *Practicality:* Duration of MCC test (minutes), Technician “learning curve,” Clinical Staff and Patient Satisfaction, Duration of fasting required
- 3) *Integration:* Scheduling MCC, Linkage with EGD follow-up, Image storage, Image transfer, Documentation of Interpretation, Photo-documentation, Database development

Aim 2: High-Quality Visualization (90%) of Gastric Anatomic Landmarks

Defined as visualization and photo-documentation of the following anatomical landmarks:

- 1) Lower Esophagus / Z line
- 2) Cardia / fundus
- 3) Body, lesser curvature AND/OR Body, greater curvature
- 4) Anterior / Posterior walls
- 5) Angularis
- 6) Antrum
- 7) Pylorus
- 8) Duodenal Bulb
- 9) Duodenal Ampulla

Aim 3: MCC versus EGD for visualization of anatomic landmarks (see above) and gastric lesions in symptomatic patients

Defined as visualization and photo-documentation of the following structures and diseases:

- 1) Visible Lesions (Paris Classification if relevant)
- 2) Ulcers (Forrest Classification) erosions
- 3) Gastric Atrophy
- 4) Gastric Varices
- 5) Gastritis*
- 7) Submucosal lesions
- 8) “Does patient need a follow-up EGD?” Y/N (Opinion of endoscopist interpreting MCC based on MCC findings.)

* (not erythema but ‘chicken wire’ pattern intramucosal change in vascular pattern or hemorrhagic)

8.2. Secondary Outcomes:

- (1) Cost-effective analysis

- (2) 30-day follow-up for adverse events and safety
- (3) Patient Satisfaction of MCC versus EGD
- (4) Replication of similar sensitivity and specificity of MCC to EGD to prior trials outside of the US for (a) Ulcers; (b) Cancer; (c) Inflammatory Changes
- (5) Time spent visualizing the stomach for MCC versus EGD (minutes)
- (6) Visualization of the duodenum
- (7) Hiatus hernia

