6.3. Potential Risks and Benefits

6.3.1. Potential Risks

Patients for whom study enrollment may interfere with standard clinical care will not be enrolled. Alternatives to study participation are for patient to receive standard of care treatment for symptoms which includes only an EGD or barium studies. We have considered a variety of potential risks to participants including cognitive, affective,

physical, legal/confidentiality and economic risks. The NaviCam MCC is manufactured by AnX Robotica and has been granted marketing authorization by the FDA through the de-novo process to confirm its safety and effectiveness profile.

Since its introduction to the Chinese market after being approved by the Chinese Food and Drug Agency (CFD) in 2012, the NaviCam MCC was subject to a series of clinical studies. Published studies involving more than 500 people in China have been published comparing MCC to gastroscope. In a pilot study in 34 healthy volunteers (Liao et al. 2012), 75 to 100% of gastric mucosa was visualized in 27 (79.4%) people and 50% to 75% in 7 (20.6%) people. Visualization of the gastric cardia, fundus, body, angulus, antrum and pylorus were subjectively assessed as complete in 82.4%, 85.3%, 100.0%, 100.0%, 100.0% and 100.0% respectively. In a non-blinded comparative study in 68 patients (Zou et al. 2015) showed a diagnostic accuracy similar to standard gastroscopy: the positive percent agreement was 96.0%, and the negative percent agreement was 77.8%. The overall agreement was 91.2% with a κ value of 0.765 ($p<0.001$). A total of 68 pathological findings were detected, of which 53 were identified by both methods. In a multi-center comparative study in 350 patients (Liao et al. 2016), the NaviCam detected gastric focal lesions in the whole stomach with 90.4% sensitivity, 94.7% specificity, a PPV of 87.9%, a NPV of 95.9% and 93.4% accuracy. The NaviCam was preferred by almost all patients (95.7%), compared with gastroscopy. (Liao, 2016).

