8.3.3. Fasting and MCC prep

- NPO Midnight the day before MCC.

8.3.4. Scoring Anatomic Regions.

After confirming that gastric emptying has been achieved with overnight fast -- we will use the 5-point visualization score described in Ching, 2019 for the following anatomic regions

- Lower Esophagus / Z line
- Corpus
 - Greater curvature
 - Lesser Curvature
- Anterior Wall
- Posterior Wall
- Proximal stomach
 - Cardia/Fundus
- Distal Stomach
 - Antrum/Pylorus/Angularis
- Duodenum
 - Bulb
 - Ampulla

8.3.5. Scoring Gastric Mucosal lesions.

("yes/no")

- Visible Lesions (Paris Classification if relevant)
- Ulcers (+/- Forrest Classification)
- Gastric Atrophy
- Gastric Varices
- Gastritis*
- Hiatus hernia
- Submucosal lesions
- Plus: Does patient need endoscopic intervention?

8.3.6. Lesions picked up by MCC and not by EGD.

- Healing lesions (especially ulcers) are natural course of disease therefore we assume that some

lesions will be detected by capsule but not by EGD if EGD is done a few days later. With photo-documentation and two independent readers, we hope to assure that this phenomenon is a natural course of lesion and not a "false-positive" by MCC.

8.3.7. Measuring patient satisfaction (see *MAGNET7 and 8, day 7 and 30*).

- I felt the research team answered all my questions. Yes No
- Did you feel any pain with swallowing? Yes No
- How difficult was it to swallow the capsule? Very Easy Moderately Easy Neutral Moderately Difficult Very Difficult
- Did you feel discomfort after swallowing while operator moved the capsule? Yes No
- Did you notice the capsule pass during a bowel movement?? Yes No
- Any other issues? Yes No
- If yes, what were the issues? _____
- How much time in total approximately did you have to take out during your day for the capsule endoscopy procedure? _____ (we do not ask this)
- Did you feel like you needed to miss work after the capsule endoscopy procedure? Yes No (we do not ask this)
- Did you need someone to take you home after the capsule endoscopy procedure? Yes No (we do not ask this) In the future, if both studies were equally accurate and you needed another examination of your stomach, would you prefer to have a traditional EGD or a capsule? EGD Capsule. Why?

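### Secondary outcome 8.2(4) calls for cancer sensitivity and specificity, but the protocol's lesion lists name no cancer item, its quoted benchmarks are pooled, and 72 patients would yield about one cancer or none

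*Protocol*

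**What the plan says.** Section 8.2(4) of the protocol asks that the sensitivity and specificity of MCC against EGD replicate those of "prior trials outside of the US for (a) Ulcers; (b) Cancer; (c) Inflammatory Changes". The matching objective, 7.2(4), has no split by disease: "To compare international trials that compared EGD to MCC for detection of gastric lesions".

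The scored lesions are listed in 8.1 (Aim 3) and again, as yes/no items, in 8.3.5. Ulcers have their own item, "Ulcers (+/- Forrest Classification"). Gastritis also has one, with a footnote in 8.1 that narrows it: "not erythema but ‘chicken wire’ pattern intramucosal change in vascular pattern or hemorrhagic". The other lesion items are atrophy, varices, submucosal lesions and the general item "Visible Lesions (Paris Classification if relevant"); 8.3.5 adds hiatus hernia. Neither list names cancer or malignancy.

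Prior accuracy appears only in 6.3.1. In the 350-patient multi-center study the device "detected gastric focal lesions in the whole stomach with 90.4% sensitivity, 94.7% specificity, a PPV of 87.9%, a NPV of 95.9% and 93.4% accuracy". The 68-patient comparative study is summarised by positive agreement of 96.0%, negative agreement of 77.8%, overall agreement of 91.2% and a kappa of 0.765. Neither result is split by lesion type.

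Section 13.2 states that 72 is a practical number, that no formal inference is planned, and that patients with incomplete gastric emptying are left out of the accuracy assessment.

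**The concern.** An outcome that sets sensitivity and specificity beside earlier results needs three things: a recorded variable for each disease class, a comparator on the same definition, and enough reference-positive patients for the estimate to carry information. For cancer, the protocol's lists do not supply the first, its quoted figures do not supply the second, and 72 patients are unlikely to supply the third. For ulcers and inflammatory changes the variables exist, but the protocol quotes no class-specific figure to set them against, and the sensitivity estimates will be wide.

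At stake is how this outcome will be read. A result such as one cancer found out of one, reported as replication of earlier accuracy, would claim far more than the data hold. Meanwhile the one comparison that the quoted figures permit, for pooled focal lesions, is not the one the outcome sets.

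**Working it through.** **1. The three classes against the lists and the quoted figures**

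| Class in 8.2(4) | Item in 8.1 / 8.3.5 | Accuracy figure quoted for that class |
|---|---|---|
| Ulcers | Yes (8.1 adds erosions, 8.3.5 does not) | None |
| Cancer | None named; the visible-lesions item does not separate it | None |
| Inflammatory changes | Gastritis, narrowly defined; not stated to be the same thing | None |
| Gastric focal lesions pooled (not in 8.2(4)) | Could be built from the 8.3.5 items; not defined | 90.4% / 94.7% |

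**2. Reproducing the quoted figures**

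An integer search for a 2x2 table on 350 patients gives one table that fits all five percentages: 104 positive and 246 negative. It gives sensitivity 94/104 = 90.4%, specificity 233/246 = 94.7%, PPV 94/107 = 87.9%, NPV 233/243 = 95.9% and accuracy 327/350 = 93.4%. The exact 95% intervals are 83.0% to 95.3% for sensitivity and 91.1% to 97.2% for specificity. The 68-patient study fits 48/50 = 96.0%, 14/18 = 77.8% and 62/68 = 91.2%, with kappa 0.765. Both sets are internally consistent, and each is a single pooled table.

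**3. Expected cancers among 72 patients**

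The protocol gives no prevalence by disease, so 0.5% to 2% is an assumption. The expected number is 72p and the chance of none is (1 − p)^72.

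| Assumed p | Expected cases | Chance of none |
|---|---|---|
| 0.5% | 0.36 | 0.995^72 = 0.70 |
| 1% | 0.72 | 0.99^72 = 0.48 |
| 2% | 1.44 | 0.98^72 = 0.23 |

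With no case, sensitivity is undefined. If every case is detected, the exact (Clopper-Pearson) lower limit is 0.025^(1/n): 2.5% for 1 of 1 and 16% for 2 of 2, with an upper limit of 100% in both.

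**4. Ulcers, gastritis and a pooled class**

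The exact limits for x of n are the 2.5% point of Beta(x, n − x + 1) and the 97.5% point of Beta(x + 1, n − x). Cell counts are rounded, with sensitivity near 90.4% and specificity near 94.7%. Section 6.2 says that up to 70% of procedures without alarm symptoms show nothing significant, so 30% is a reasonable trial value for a pooled class; the benchmark had 104/350 = 29.7%. The 10% for a single class and the 25% loss of evaluable pairs are assumptions.

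| Patients | Prevalence | Sensitivity (95% CI) | Specificity (95% CI) |
|---|---|---|---|
| 72 | 30% | 20/22 (70.8% to 98.9%) | 47/50 (83.5% to 98.7%) |
| 72 | 10% | 6/7 (42.1% to 99.6%) | 62/65 (87.1% to 99.0%) |
| 54 (25% loss) | 30% | 14/16 (61.7% to 98.4%) | 36/38 (82.3% to 99.4%) |

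Even 7 of 7 has a lower limit of 59%. By the normal approximation, a half-width of 10 points needs 1.96² × 0.904 × 0.096 / 0.10² = 33.3, so 34 EGD-positive patients. A class at 30% prevalence supplies about 22.

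**The case against.** The strongest reply is that section 13.2 already disclaims formal inference and power, so imprecise estimates are expected in a pilot. That stands: this is not an underpowered test, because no test is planned. But a descriptive outcome still needs a recorded variable and a stated comparator, and the word chosen for this one is replication.

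Second, a reader might infer that none of the three classes has a matching measurement. The documents do not support that. Ulcers and gastritis are scored yes/no, so the missing item concerns cancer alone. Nor do they show that cancer goes unrecorded. Section 8.3 refers to data collection sheets, and forms Magnet 4 to 6 are not shown, so the claim is limited to the protocol's own lists. The visible-lesions item could also hold a suspected cancer without identifying it as one.

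Third, a reader might infer that a histological reference is required. It is not: the outcome compares MCC with EGD, and EGD is the stated reference.

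Fourth, the outcome refers to prior trials in the plural and does not name the 350-patient study as its benchmark. The cited papers may hold results by lesion type. What can be said is that the protocol quotes none.

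Finally, specificity is reasonably estimable. This too stands, and the precision problem is one of sensitivity.

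**Conclusion.** The point holds in limited form. Section 8.2(4) names cancer as an accuracy class while the protocol's lesion lists do not, its own objective refers only to gastric lesions, and every accuracy figure it quotes is pooled. Under the assumed prevalence of 0.5% to 2%, the chance of seeing no cancer is 70% to 23%, and one or two cases would give an interval starting at 2.5% or 16%. Ulcer and gastritis sensitivity are measurable but imprecise, at 42% to 99.6% for 6 of 7 under an assumed 10% prevalence. Specificity is adequate for description, at 87% to 99% in the same setting.

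Disease prevalence and loss of evaluable pairs are assumptions, but the conclusion for cancer holds across the range shown. The effect is confined to one secondary outcome in a pilot: neither the sample size nor the primary aims depend on it. It is worth correcting because the correction costs little and brings the outcome into line with section 13.2.

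**What to change.** Reword 8.2(4) as follows.

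- **Main analysis:** per-participant sensitivity and specificity of MCC against EGD for pooled gastric focal lesions, with exact 95% intervals, set descriptively beside the quoted 90.4% and 94.7%. The protocol does not define a focal lesion, so state in advance which 8.3.5 items count. Visible lesions, ulcers and submucosal lesions are an obvious starting set. Decide explicitly on erosions, gastritis, atrophy and varices, and check the choice against the definition in the benchmark paper.
- **Exploratory:** ulcers and gastritis, the latter named as the item for inflammatory changes, each with counts, sensitivity, specificity and exact intervals.
- **Cancer:** drop sensitivity and specificity. List each suspected cancer with the MCC reading, the EGD finding and the routine-care biopsy result where one exists.
- **Wording:** replace replication with descriptive comparison, and align objective 7.2(4) with the new text.

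This is a wording change on data that the protocol already plans to collect. The cost is a cancer accuracy claim that the trial could not have supported. The pooled estimate will itself be wide, about 71% to 99% for sensitivity at 30% prevalence, and should be reported as such.

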8.3. Selected Outcomes Measures (see data collection sheets)

8.3.1. Procedure time.

- When measuring procedure time of EGD and MCC, we will consider all components of procedure including anesthesia, prep, cleaning and preparing room for next patient and turn-around time. We will also measure total time for staff and for the clinician.

8.3.2. Training to perform MCC.

- How long? How many cases needed? Is there a learning curve to speed and accuracy?

8.3.3. Fasting and MCC prep

- NPO Midnight the day before MCC.

8.3.4. Scoring Anatomic Regions.

After confirming that gastric emptying has been achieved with overnight fast -- we will use the 5-point visualization score described in Ching, 2019 for the following anatomic regions

- Lower Esophagus / Z line
- Corpus
 - Greater curvature
 - Lesser Curvature
- Anterior Wall
- Posterior Wall
- Proximal stomach
 - Cardia/Fundus
- Distal Stomach
 - Antrum/Pylorus/Angularis
- Duodenum
 - Bulb
 - Ampulla

8.3.5. Scoring Gastric Mucosal lesions.

("yes/no")

- Visible Lesions (Paris Classification if relevant)
- Ulcers (+/- Forrest Classification)
- Gastric Atrophy
- Gastric Varices
- Gastritis*
- Hiatus hernia
- Submucosal lesions
- Plus: Does patient need endoscopic intervention?

8.3.6. Lesions picked up by MCC and not by EGD.

- Healing lesions (especially ulcers) are natural course of disease therefore we assume that some

lesions will be detected by capsule but not by EGD if EGD is done a few days later. With photo-documentation and two independent readers, we hope to assure that this phenomenon is a natural course of lesion and not a "false-positive" by MCC.

8.3.7. Measuring patient satisfaction (see *MAGNET7 and 8, day 7 and 30*).

- I felt the research team answered all my questions. Yes No
- Did you feel any pain with swallowing? Yes No
- How difficult was it to swallow the capsule? Very Easy Moderately Easy Neutral Moderately Difficult Very Difficult
- Did you feel discomfort after swallowing while operator moved the capsule? Yes No
- Did you notice the capsule pass during a bowel movement?? Yes No
- Any other issues? Yes No
- If yes, what were the issues? _____
- How much time in total approximately did you have to take out during your day for the capsule endoscopy procedure? _____ (we do not ask this)
- Did you feel like you needed to miss work after the capsule endoscopy procedure? Yes No (we do not ask this)
- Did you need someone to take you home after the capsule endoscopy procedure? Yes No (we do not ask this) In the future, if both studies were equally accurate and you needed another examination of your stomach, would you prefer to have a traditional EGD or a capsule? EGD Capsule. Why?

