4. PROTOCOL SUMMARY

Title:	Magnetically Controlled Capsule For Assessment Of Gastric Mucosa In Symptomatic Patients: “MAGNET”
Précis:	This is a single-center prospective study examining the diagnostic utility of a single-use ingestible magnetically controlled capsule (MCC) endoscope (NaviCam™, AnX Robotica) which is remotely controlled by external hardware and software to visualize the mucosa of the stomach on patients with upper abdominal symptoms. Participants will be enrolled and tested at a central site referred from Emergency Departments (EDs), urgent cares (UCs) and primary care practices (PCPs) in the Washington, DC area and additional site(s) to be named. Total enrollment is estimated to be 72 patients with a goal of following all patients with a traditional endoscopy to confirm findings. Aim 1 is to establish feasibility of this novel outpatient testing. Aim 2 is to demonstrate high-quality visualization of gastric anatomic landmarks. Aim 3 is a pilot study to compare visualization of gastric anatomic landmarks and lesions of MCC follow-up traditional EGD. We currently anticipate enrolling 2-3 patients per week over 30 weeks.
Objectives:	
Aim 1: We aim to demonstrate feasibility of MCC in an outpatient primary and urgent care setting. Measured outcomes include duration of MCC test, linkage with EGD follow-up, image storage, image transfer, technician learning curve and documentation.
 
Aim 2: We aim to show that MCC can identify and photograph regions of stomach consistent with established visualized scoring systems for anatomic landmarks.
 
Aim 3: Pilot assessment of MCC compared to subsequent EGD to detect anatomic regions and gastric mucosal lesions.

Population:	An unselected pool of adult patients with an appropriate indication for upper endoscopy such as epigastric pain/burning, nausea and or vomiting, bloating, heartburn, iron deficiency anemia, unintended weight loss, abnormal imaging suggesting organic disease. In general, participants will be age ≥ 18 , mixed gender, mixed race, hemodynamically stable with possible co-morbidities.
Site Number	1
Study Duration:	Time needed to reach sufficient study subjects plus additional time for analysis
Subject Duration:	30 days
Estimated Time to Complete:	12 months

5. SCHEMATIC OF STUDY DESIGN:

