will be pre-determined, and each area will have a predetermined number of images obtained as suggested by Gastroenterology Society guidelines.

5. Patient data collected will include the following elements: chief complaint of patient, history of present illness, past medical history, current medications (only PPIs and pain medication)..
6. At completion of MCC, video will be archived and patient satisfaction will be assessed. Capsule endoscopy will NOT be used for clinical decisions.
7. Patients will be instructed to return to the physician sooner, if concerning signs develop. A 7 and 30-day follow-up call and chart review is only performed if person is lost to follow-up will be conducted to check for symptom resolution and adverse events.
8. Esophagogastroduodenoscopy (EGD) will be performed as soon as possible in an appropriate endoscopy facility by an experienced endoscopist.
9. Endoscopic images will be stored in secure serve for later comparison with MCC images.

Summary of Research Strategy

- ❖ PRE-SCREEN (DAY -7 to DAY -1)
 - Upper Abdominal Pain or Related Symptoms (Indications for an EGD)
 - Performed in ED, UC, PCP offices or GI clinic
- ❖ SCREEN (DAY -7 -> DAY 0)
 - More thorough screening questions and scheduling by RC (<24 hours)
 - Performed by Telephone
- ❖ ENROLL (DAY 0)
 - Signed Informed Consent procedure, more detailed questions and MCC Procedure performed
 - Occurs at the GWU Medical Faculty Associates Building on [name].
 - NaviCam MCC performed by trained Clinician.
 - Reviewed by a Gastroenterologist.
 - Scheduled for an EGD will ideally be performed within 5 days of the MCC procedure, but will allow MCC procedure to be performed up to 14 days either before or after an EGD (paid by insurance as standard of care).
- ❖ FOLLOW-UP (DAY 1-30)

- Day 7 and Day 30: Telephone Call plus CRISP Chart Review, only if lost to follow-up.

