13.2. Sample Size Considerations

The sample size for this Proof of Concept study was not chosen for statistical consideration, as there are no formal statistical inferences planned. The size of the study is judged adequate for the preliminary evaluation objectives. All 72 participants will receive the MCC and will be referred to follow-up EGD. The base-line prevalence of lesions and the estimated loss to follow-up will provide information for formal sample size calculation for follow-up study.

We did not use a statistical justification but a practical justification to choose 72 participants. All 72 will get the MCC unless they are unable to tolerate the capsule. The issue of drop-out is relevant only to Aim 3 which pilots the concept of non-inferiority compared to subsequent EGD. We did not power this study to prove non-inferiority --- this study will allow us to estimate baseline lesion prevalence and the likely drop-out rate. Moving forward, we will be able to calculate an accurate sample size for a future larger definitive non-inferiority study.

For patients in whom visualization is limited by incomplete gastric emptying, we will record fasting time but exclude patient from assessment of MCC accuracy.

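### Section 8.3.6 relies on photographs and two readers to show that capsule-only lesions have healed. They cannot show this, and only one direction of disagreement is addressed.

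*Protocol*

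**What the plan says.** Section 8.3.6 deals with lesions found by MCC and not by EGD. It treats healing, especially of ulcers, as the expected explanation for some of them: "lesions will be detected by capsule but not by EGD if EGD is done a few days later". It then offers its safeguard: "With photo-documentation and two independent readers, we hope to assure that this phenomenon is a natural course of lesion", as opposed to a false positive of the capsule.

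Three other places bear on this:

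- **Section 9.4, Summary of Research Strategy.** The aim is an EGD within 5 days of MCC, but the protocol "will allow MCC procedure to be performed up to 14 days either before or after an EGD".
- **Section 9.4, item 9.** "Endoscopic images will be stored in secure serve for later comparison with MCC images". No rule says how the comparison is used for discordant cases.
- **Section 8.2, outcome 4.** "Replication of similar sensitivity and specificity of MCC to EGD to prior trials outside of the US", for ulcers, cancer and inflammatory changes.

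No section discusses lesions found by EGD and not by MCC.

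**The concern.** An MCC-only lesion has more possible explanations than the two that 8.3.6 names, and the tools it relies on do not distinguish among all of them. The section also leans towards the explanation that favours the capsule, and only for the kind of disagreement that lowers the capsule's specificity. The counterpart, an EGD-only lesion that healed before a later MCC, receives no such allowance.

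What is at stake is the descriptive specificity of MCC against EGD and its comparison with earlier trials. If MCC-only cases were excused after the results are known, the estimate could move in one direction only. It would also no longer be like for like with studies that counted such cases against the capsule.

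**Working it through.** **1. What two-reader agreement can show.** Take a lesion that MCC reports and EGD does not.

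| Explanation | Does agreement of two MCC readers bear on it? |
|---|---|
| One reader misread the image | Yes, the second reader can expose it |
| Both readers misread the same image | No, they agree |
| Real lesion, healed before a later EGD | Agreement supports that it was real, not that it healed |
| Real lesion, missed at EGD | Same agreement, so not separable from healing |

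The second row can be put in figures. With a false-positive rate p per reader and correlation ρ between their errors, both are wrong with probability p² + ρp(1 − p). For an assumed p of 10% (not a protocol figure):

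- ρ = 0: 0.01, or 1%
- ρ = 0.6: 0.01 + 0.6 × 0.09 = 0.064, or 6.4%
- ρ = 1: 0.01 + 0.09 = 0.10, or 10%

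The gain from a second reader therefore depends on how far errors are shared through the same images.

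**2. Test order.** In MCC-first pairs, healing between the tests yields MCC-only lesions. In EGD-first pairs it yields EGD-only lesions. Section 9.4 allows both orders; section 8.3.6 speaks only to the first.

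**3. How a cited study counted such cases.** The figures that section 6.3.1 gives for the 68-patient study are positive agreement 96.0%, negative agreement 77.8%, overall agreement 91.2% and κ 0.765. They fit a single 2×2 table: 48 both positive, 2 EGD-only, 4 MCC-only, 14 both negative. Negative agreement is 14/18 = 77.8%, so its 4 MCC-only cases counted against the capsule.

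**4. Size, if an MCC-only patient were set aside.** Specificity goes from TN/(TN + FP) to TN/(TN + FP − 1), which can only be higher.

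Inputs:
- 72 patients (section 13.2), and 50 to 72 completed pairs (assumption).
- 70% EGD-negative: the upper figure in section 6.2, for patients without alarm symptoms, used as an assumption. This gives 50 of 72, or 35 of 50. All pairs EGD-negative stands in for a rare lesion type.
- Specificity 94.7% or 77.8%, from the two comparative studies in section 6.3.1, rounded to whole patients.

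| EGD-negative | Before | One set aside | Rise (points) |
|---|---|---|---|
| 50 (70% of 72) | 47/50 = 94.0% | 47/49 = 95.9% | 1.9 |
| 50 (70% of 72) | 39/50 = 78.0% | 39/49 = 79.6% | 1.6 |
| 35 (70% of 50) | 33/35 = 94.3% | 33/34 = 97.1% | 2.8 |
| 35 (70% of 50) | 27/35 = 77.1% | 27/34 = 79.4% | 2.3 |
| 72 (all of 72) | 68/72 = 94.4% | 68/71 = 95.8% | 1.3 |
| 72 (all of 72) | 56/72 = 77.8% | 56/71 = 78.9% | 1.1 |

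With all of 50 pairs EGD-negative, the counts and rises are those of the first two rows. The range is 1.1 to 2.8 points per patient.

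**5. Against sampling error.** Exact (Clopper-Pearson) 95% intervals are 83.5% to 98.7% for 47/50 and 64.0% to 88.5% for 39/50, so one patient's shift is a small fraction of either width.

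**The case against.** The strongest reply is that 8.3.6 fixes no analysis rule. It assumes something about some lesions and expresses a hope. A reader might infer that MCC-only cases will be recoded or removed; no section says so. This stands, and it is why the bias is only a risk. Tabulation and sensitivity analyses may also sit in an unseen SAP. That is fair for the detail, but the inference from two readers to natural course is written in the protocol and does not follow.

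Second, in a healed lesion and in an EGD miss alike, the capsule reading was right, so separating them matters little for whether MCC erred. This stands in part. What remains is the shared misreading, and the fact that the section claims to establish natural course specifically. Photographs, independent readers and stored EGD images do have value against error.

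Third, some stronger readings are tempting but not supported:

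- That EGD-first pairs falsify the premise of 8.3.6. They do not: the sentence is conditional on a later EGD, so these pairs fall outside it. The section is silent on them, not wrong about them.
- That 8.3.6 contradicts the summary's aim of EGD follow-up "with a goal of following all patients with a traditional endoscopy to confirm findings". Seeking confirmation is compatible with accepting that a later test may miss a transient lesion.
- That sensitivity would be inflated by excusing EGD-only lesions. The protocol nowhere proposes this; with EGD as comparator they count by default as capsule misses.
- That the lesion prevalence carried to the next trial under section 13.2 is inflated. That would need MCC-only findings to be relabelled as true lesions, which is not stated.

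**Conclusion.** The point holds as a minor one. Section 8.3.6 credits photographs and two readers with more than they can show, and its allowance for healing covers one discordant direction although the protocol permits both test orders.

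If the section were used to set aside MCC-only patients, specificity against EGD would rise by about 1 to 3 points for each one. This rests on the assumed 50 to 72 pairs, at least 70% EGD-negative, and the specificities of the cited studies. It is an any-lesion illustration, since the protocol gives no figures by lesion type. A lower EGD-negative share is possible, because anemia and weight loss qualify for entry, and the shift per patient would then be larger.

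The shift is small against sampling error, but unlike sampling error it always favours the capsule. Section 13.2 plans no formal inference, so no error rate or decision rule is affected; only descriptive accuracy estimates are.

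**What to change.** Replace the last sentence of section 8.3.6 with a statement that:

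1. the main sensitivity and specificity use EGD as the fixed reference, with no relabelling or removal of discordant findings;
2. MCC-only and EGD-only findings are both tabulated by test order and by MCC-EGD interval;
3. possible healing is shown only as a labelled sensitivity analysis, applied to MCC-only lesions in MCC-first pairs and to EGD-only lesions in EGD-first pairs.

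The cost is one rewritten passage and one small table built from the two procedure dates. No extra readers, visits or patients are needed. The downside is that some true healing counts as capsule error in the main estimate, although the sensitivity analysis shows how much, and that the cells by order and interval will be small.
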